Both researchers and study participants will be blinded to the order in which the interventions will be given. The blinding process will be conducted by an independent researcher of the study team. This is done in order to avoid any bias when analysing the data. Unblinding of the study interventions will be done by the same researcher who was involved in the blinding process and it will be done at the end of the clinical study which is after the last study visit of the last participant.

Emergency unblinding will only be conducted in medical emergencies when the appropriate management of the participant necessitates knowledge of the treatment, or in the event that expedited reporting to the Research Ethics Committee (REC) of an unexpected and related Serious Adverse Event (SAE) is required. In the event that emergency unblinding of an individual participant is required, authorised members of the research team will follow trial procedures to unblind the participant in question and proceed with expedited reporting if required. Unblinding should only be considered if

management of the participant would differ depending on whether they were on placebo intervention (cellulose) or dietary fibre intervention (fibre mix of inulin, pectin and oat beta-glucan).

Randomization of study participants to the order in which they will receive the intervention products (placebo and dietary fibre) will be done by SealedEnvelope.com Participants will take the dietary supplements twice daily over 28 days in the order outlined below:

10g/day (5g morning or lunch and 5g dinner) from day 1 to day 4 20g/day (10g morning or lunch and 10g dinner) from day 5 to day 12 30g/day (15g morning or lunch and 15g dinner) from day 13 to day 28

After the wash-out period, the same procedure as above will be repeated but participants will consume the opposite arm of the intervention. For example, if in the first four weeks of the intervention period of the study, they consumed the placebo product, in the second four weeks of the intervention period of the study, they will consume the dietary fibre product.

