Afterwards, they will have a blood test to check they are not anaemic or diabetic and height and weight measurements will also be taken. They will also have an electrocardiogram (ECG) and blood pressure will be recordedtaken. All women of childbearing age will have a pregnancy test. Participants will also be asked to complete, together with the researcher taking consent, a brief questionnaire assessing their eligibility for the study. Specifically, their weight, height, blood pressure, the result of the pregnancy test will be recorded, as well as any information related to family history of disease, or any medication they are currently taking. In addition, personal information, such as their address (for the collection kits to be sent over), GP details, next of kin will be recorded.

They will also be explained how to use the urine and stool collection kits. Fasted urine and stool samples will be collected by study participants on the day when they come for each study visit. If the results of the blood test will make participants eligible for the study, they will be sent by post the urine and stool collection kits which they will use to bring their samples in on the first study visit. If the blood tests results indicate that they are not eligible for the study, participants will be informed (either by phone or e-mail) by a member of the research team that they will not be able to participate in the study because they do not fit the eligibility criteria.

During the health screening visit, participants will also be explained how to complete the 3 days food diary. If the results of the blood test will make participants eligible for the study, they will be sent by post the first 3 days food diary which they will bring filled in with what they ate and drank 3 days before the first study visit. Eligible participants (once the blood tests results will come and indicate that participants are eligible to participate) will also be sent by post a questionnaire related to demography and dietary habits.

Participants will be advised not to start any strenuous physical activities or go on new diets as these may lead to conflicting results. They will also be asked to consume a similar evening meal the day before each study visit (to ensure consistency between study visits), avoid alcohol the day before each study visit and fast overnight (for 12h) before each study visit (drinking water will be fine).

Visits 1, 2, 3 and 4– Study Visits

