There is a 4-week gap (28 days +/-4 days) between Study Visits 1 and 2, followed by a 4-week wash-out period (28 days +/-7 days) and then followed by Study Visits 3 and 4 (4-week gap 28 days +/-4 days between Study Visits 3 and 4) (Figure 1).

[figure not shown]

Figure 1. Diagram of study visits; V=study visit

Participants will come fasted at the Study Visits and they will not have consumed any intervention products in the morning. They will bring their stool and urine samples, the 3 days food diaries and the participants questionnaire. They will also undergo a physical examination (body weight, height and fat percentage) and have their blood pressure measured and recorded. Women of childbearing age will have a pregnancy test at the beginning of each study visit. If the pregnancy test result is positive, they will be withdrawn from the study. No more data and samples will be collected from them. All the data and samples that were collected up to their withdrawal will be used in data analysis.

At Study Visits 2 and 4 participants will be asked to complete a Visual Analogue Questionnaire where they will rate how the dietary intervention has affected various gastrointestinal symptoms, such as constipation, bloating, appetite.

At 09:30 an intravenous cannula will be inserted into one arm for blood sampling by an adequately trained doctor, nurse or member of research team under aseptic conditions. Just before 10:00 fasting blood samples will be taken through an intravenous peripheral cannula (-15min and -5min). Participants will then receive a standardised breakfast at 10:00.

Postprandial blood samples will be taken at 15, 30, 45, 60, 90, 120 180 and 240 minutes after having the standardised breakfast to measure gut hormones, lipids, glucose, and insulin and inflammatory marker levels. 10ml of blood samples will be

taken at each sampling point, and therefore 100ml (10 x 10ml) during each study visit will be taken (Figure 2).

[figure not shown]

Figure 2. Diagram of Study Visit protocol; VAS=Visual Analogue Scale

Appetite and wellbeing will be assessed at the following timepoints (Figure 2): -15, 0, 30, 60, 120,180 and 240 minutes using a visual analogue scale (VAS).

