The collected samples (stool, urine and blood) will be analysed for: gut microbiota composition (from stools) through 16S rRNA sequencing and qPCR (quantitative Polymerase Chain Reaction); metabolites produced by the gut microbiota (from stools and urine) thorough NMR (Nuclear Magnetic Resonance), GC-MS (gas chromatography coupled with mass spectrometry), LC-MS (liquid chromatography coupled with mass spectrometry), LC-MS (liquid chromatography coupled with mass spectrometry), blood glucose, insulin, gut hormones (PYY and GLP-1), inflammatory markers (C reactive protein) and lipid levels.

11. Statistical Analysis

Statistical tests, such as ANOVA (Analysis of Variance) and t-tests (paired and unpaired) will be used to compare different groups: study participants groups, dietary fibre groups and placebo groups. Correlation analysis (Pearson and/or Spearman) and linear models will be used to analyse the relationship between gut bacteria taxa, short-chain fatty acids levels, metabolites levels, food diary information and demographics. Statistical significance levels will be p<0.05.

Various platforms will be used to analyse the data. Gut microbiome composition will be analysed using 16S rRNA sequencing on Illumina MiSeq and statistical analyses will be performed in R. Species diversity and richness will be calculated and statistical tests include t-tests and Mann-Whitney U tests, statistical significance p<0.05. Species diversity and richness and their changes from baseline between grandmother, mother and offspring will be compared. Data from placebo and dietary fibre intervention will be compared.

Short-chain fatty acids (SCFA) production from stool samples will be measured using GC-MS (Gas Chromatography coupled with Mass Spectrometry). T-tests (paired and/or unpaired) and ANOVA tests will be used to determine whether there are significant differences in SCFA production between grandmothers, mothers and offspring from baseline to end of intervention. Data from placebo and dietary fibre intervention will be compared. Significance levels will be p<0.05.

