NMR analysis will be done on urine and stool samples to examine and compare metabolic profiles between grandmothers, mothers and offspring and their changes from baseline to end of intervention. Multivariate data analysis, such as Principal Component Analysis will be used to examine and compare if there are chemicals that differentiate the profiles of grandmothers, mothers and offspring at baseline and at the end of intervention. Analyses will be done using the following software R, Matlab, Simca and Prism GraphPad.

Food diaries will be coded using the Dietplan software which will offer insight into participants dietary habits such as their macronutrient intake. The data will be analysed using ANOVA, t-tests in R and Prism GraphPad to examine potential differences and similarities between participants.

The PhD student will be assisted by [name] in analysing the data. She will only have access to anonymised data.

12. Withdrawal Criteria and Adverse Events

Withdrawal Criteria

The safety of the study participants takes priority. Any significant adverse event (as assessed by the researchers) will halt the study and the ethics committee and sponsor will be informed as per standard protocol. All adverse events will be recorded and investigators will review each adverse event as it arises. In addition, participants will be free to withdraw at any time and are not required to give a reason.

If one or two participant(s) of the study group decide(s) to withdraw or need(s) to be withdrawn from the study, the other participant(s) from the group can still continue to participate.

The researcher can withdraw the participant on any of the following grounds:

• Participant's request

- Participant is lost to follow-up
- Participant no longer fulfils the eligibility criteria during the study duration (e.g. participant becomes pregnant etc.)
- Participant develops a condition or illness that interferes with participant's ability to take part in the study
- The investigator reserves the right to withdraw participants in the interest of participant's safety and welfare
- The participant loses capacity to consent.

All data and samples that have been collected up to the withdrawal point will be analysed and used in the study. After withdrawal from the study, no more samples and data will be collected from the participant.

Adverse Event (AE): Any untoward medical occurrence in a patient or clinical study subject.

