Incidental findings are defined as results that are outside the original purpose for which a test or procedure was conducted. Incidental findings can be either "anticipatable" or "unanticipatable." An anticipatable incidental finding is one that is known to be associated with a test or procedure. Anticipatable incidental findings need not be common or even likely to occur—their defining characteristic is that the possibility of finding them is known. Unanticipatable incidental findings include findings that could not have been anticipated given the current state of scientific knowledge. All such incidents will be reported to the participants and recorded in participant's file document. The Chief Investigator, and clinical care team of the clinical trial will also be informed of this. If the incidental finding affects the wellbeing and welfare of the participant, they will be assessed immediately by a trained clinician part of the hospital.

13. Regulatory Issues

Ethics Approval

The Study Coordination Centre has obtained approval from the Research Ethics Committee (REC) and Health Research Authority (HRA). The study must also receive confirmation of capacity and capability from each participating NHS Trust before accepting participants into the study or any research activity is carried out. The study will be conducted in accordance with the recommendations for physicians involved in research on human subjects adopted by the 18th World Medical Assembly, Helsinki 1964 and later revisions.

Informed Consent

Consent to enter the study must be sought from each participant only after a full explanation has been given, an information leaflet offered, and time allowed for consideration. Signed participant informed consent should be obtained. The right of the participant to refuse to participate without giving reasons must be respected. After the participant has entered the study the clinician remains free to give alternative treatment to that specified in the protocol at any stage if he/she feels it is in the participant's best interest, but the reasons for doing so should be recorded. In such cases, the participants remain within the study for the purposes of follow-up and data analyses. All participants are free to withdraw at any time from the study without giving reasons and without prejudicing further treatment.

Confidentiality

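### Section 7 lets the code be opened after the last visit, before the SCFA data, exclusions and primary test have to be final

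*Combined protocol and SAP*

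**What the plan says.** **Blinding and unblinding (Section 7).** Researchers and participants are both blind to the order of the two products, and an independent researcher does the blinding. The stated reason is: "This is done in order to avoid any bias when analysing the data". The same researcher breaks the code, and the timing rule is: "it will be done at the end of the clinical study which is after the last study visit of the last participant". Emergency unblinding has its own rules and is not at issue.

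**When the data arise.** Section 9 (Visit 0) says: "Fasted urine and stool samples will be collected by study participants on the day when they come for each study visit". For Visits 1 to 4 it says: "They will bring their stool and urine samples, the 3 days food diaries and the participants questionnaire". Section 10 keeps visit samples frozen until they are analysed and gives no date. It also names the end of the trial and the completion of analyses as two separate conditions.

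**Primary analysis (Section 11).** "T-tests (paired and/or unpaired) and ANOVA tests will be used to determine whether there are significant differences in SCFA production", at p<0.05.

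**Which data are kept.** Three rules favour retention:
- Section 12, withdrawals: "All data and samples that have been collected up to the withdrawal point will be analysed and used in the study".
- Section 9, pregnancy: "All the data and samples that were collected up to their withdrawal will be used in data analysis".
- Section 13, alternative treatment: "the participants remain within the study for the purposes of follow-up and data analyses".

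Section 7 collects compliance data (returned sachets and a reminder sheet) but does not say how poor compliance affects the analysis. No section deals with outlying values.

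**Labels.** Under Section 13 (Confidentiality), samples carry enrolment ID and visit number. Section 11 says the person assisting the analysis sees anonymised data only.

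**The concern.** The plan states an aim, unbiased analysis, and then a trigger for unblinding that does not secure it. Once the last visit is over, the code may be opened while the last primary-outcome sample is still unassayed. Because samples are labelled by participant and visit, an opened order list identifies each one as fibre or placebo. Anonymising the data hides who a participant is, not what she was taking.

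At stake is the primary SCFA comparison. Decisions about data processing, poor compliers, outlying values and the form of the test could be made by people who can see which way each decision moves the result. With about 10 families, a single exclusion can matter.

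**Working it through.** **1. Sequence of events, from the text.**
- The unblinding condition is met once the last participant has completed Visit 4 (Section 7).
- Her Visit 4 stool is collected that same day, and her last food diary is handed in then (Section 9).
- SCFA is measured from stool by GC-MS (Section 11) after frozen storage (Section 10).
- So the primary dataset cannot be complete when the condition is met, and any full-data analysis comes after it.
- No section adds a further condition such as a data lock, a list of exclusions or a fixed model.

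**2. Size of the exposure.** The documents give no SCFA effect size or SD and no power figure, so there is nothing of the plan's own to reproduce. I used an illustration.

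From the documents: 10 families (Section 8), p<0.05 (Section 11), and a hypothesis that the older generation responds more (Section 2).

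Assumed: one older and one younger member per family, normal data, within-family correlation (ICC) 0.3, order randomised per participant, no true effect, and a two-sided paired t-test.

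For each family, d = (older member's fibre-minus-placebo change) − (younger member's fibre-minus-placebo change), scaled to SD 1. This contrast is my construct. There were 200,000 simulated trials per setting. Rejections are counted in the hypothesised direction only, so the nominal rate is 2.5%.

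Suppose the family that scores lowest on some marker is dropped, and the marker has correlation r with d. The expected shift in the mean is

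shift = r × E[maximum of 10 standard normals] / (10 − 1) = r × 1.539 / 9 = 0.171 r.

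| One family dropped | 0.171 r | Simulated shift (SD) | False positives, hypothesised direction |
|---|---|---|---|
| None | – | 0.00 | 2.4% to 2.6% |
| Order known, r = 1.0 (upper bound) | 0.171 | 0.170 | 8.8% |
| Order known, r = 0.5 | 0.086 | 0.085 | 4.3% |
| Order known, r = 0.3 | 0.051 | 0.051 | 3.5% |
| Order known, r = 0.1 | 0.017 | 0.016 | 2.7% |
| r = 0 | 0 | 0.00 | 2.5% |
| Order masked, dropped on visible period 1 minus period 2 data | 0 | 0.00 | 2.4% to 2.5% |

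Masking works because the visible period difference does not show which period was fibre. A choice based on it therefore cannot favour one direction. The masked rate also holds if order is randomised by family (2.45% to 2.60%).

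**3. Variations.**
- *Fewer families.* With 9 families: 3.4% at r = 0.3 and 8.7% at r = 1.0. With 8 families: 3.5% and 8.9%.
- *Simple fibre-minus-placebo comparison across participants.* With n = 20: 3.4% at r = 0.3 and 7.5% at r = 1.0. With n = 30: 3.3% and 6.7%. Masked, both give 2.5%.
- *Most extreme family dropped on either side.* There is no mean shift. The rate is 6.7% in each direction if extremeness is measured from the sample mean, but only 2.6% if measured from zero.
- *Better of paired and unpaired t-tests, no exclusion.* The rate is 2.6% at ICC 0.3 and 3.2% at ICC 0. Test choice between these two adds little.
- *Fully free choice.* This is a separate, smaller simulation: 10 trios, 4,000 runs, two-sided, nominal 5%. Taking the smallest p-value from paired t, unpaired t, ANOVA and the paired t with any one family removed gives 18% to 19%. Without the removal it is 5.8% to 9.3%.

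**The case against.** The strongest reply has four parts.

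- **The rule permits late unblinding.** The wording sets an earliest time. A careful team could comply and stay blind until the analysis is finished. That is true, but permission does not protect: a team that opened the code the next day would comply equally.
- **The real gap is the unwritten rules.** If the SCFA measure, model and exclusions were fixed in advance, the date of unblinding would matter little; if they stay unwritten, a later date does not define them. Much of this stands. But the rules have to be settled at some point, and the unblinding sentence decides whether that happens blind.
- **The exclusions modelled are not planned.** Every rule the protocol gives on data use keeps data. This narrows the discretion, but poor compliance and outlying values remain uncovered. The 8.8% needs deliberate removal of the least favourable family and is a bound, not a forecast. The test-choice effect is small, and Section 11 can be read as assigning paired and unpaired tests to different comparisons.
- **The consequence is limited.** Participants and researchers are blind throughout the visits, so symptom ratings, appetite scales and the ad libitum lunch are protected. GC-MS quantification is instrumental, and the study is an exploratory pilot with no power claim. All of this stands and sets the weight of the point.

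**Conclusion.** The concern holds. Section 7 makes the last visit of the last participant the only condition for routine unblinding. The primary SCFA data cannot be complete at that moment, and nothing in the protocol keeps the code closed until they are.

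The likely size is modest. Under the simulation's assumptions, one exclusion made with the order known takes the 2.5% directional error to between 2.7% and 4.3% for correlations of 0.1 to 0.5, with 8.8% as the upper bound. The correlations are assumptions; the documents support no particular value. A blind removes only the part of a correlation that comes from knowing the order. A link between, say, compliance and SCFA response that exists regardless would remain.

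The sponsor should make this change. It is a cheap improvement that serves the protocol's own stated aim, and not a fatal flaw.

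**What to change.** Replace the routine-unblinding sentence in Section 7 with a rule to this effect:

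> Routine unblinding takes place after the last visit of the last participant, and only once (a) the SCFA data are final; (b) the primary SCFA measure, the model and all exclusions, including those for poor compliance and outlying values, have been signed off by staff blind to order; and (c) that dataset is locked.

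Secondary laboratory and diary data need not delay the code if they are finalised by staff who have not been given it. Otherwise they should be finalised before release. Running the locked primary analysis on masked A/B codes is an optional extra; if used, the codes should be issued only after the lock. The emergency unblinding text stays as it is.

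**Cost.** One sentence changes, and a data lock and a short blind sign-off are added. The sign-off needs an SCFA measure, a model and an exclusion rule that the protocol does not yet define, and writing these is the main work. The independent researcher holds the code longer, and release may be somewhat later. Because the condition covers only SCFA, the primary result does not wait for the 16S, NMR or hormone assays. Visits, samples and sample size are unchanged.

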We want to investigate this hypothesis in women from 2 or 3 generations in direct link from the same family, such as grandmother, mother and daughter. At birth, mothers transmit gut bacteria to their offspring and therefore the maternal microbiome plays an important role in shaping the early composition of offspring's gut microbiota when compared to fathers. Mother's breast milk also influences the gut microbiome of their offspring in early life. However, there is little information on these maternal influences in the late life of offspring and especially in response to dietary fibre intake. Therefore, we want to determine if there is a transgenerational similarity in gut microbiome composition, metabolic profiles and clinical outcomes in response to 4-week high intake of dietary fibres compared to placebo. This approach (individuals in direct link and female participants across all generations) will allow us to 1) determine if there is a maternal influence on the gut microbiome and responses to dietary fibres of younger generations in late life and 2) have a less heterogenous cohort by focusing on women only which will allow for a better understanding of the data.

2. Study Hypothesis:

We hypothesize that compared to placebo, the dietary fibre intervention will lead to a higher production of short-chain fatty acids by the older generation's gut microbiota when compared to that of the younger generation which will translate into differential responses of gut microbiota composition, glucose, insulin, lipids, gut hormones and inflammatory markers levels.

3. Study Aim:

Investigate the effects of a dietary fibre blend taken over a 4-week period on the production of short-chain fatty acids by the gut microbiota, microbiota composition and health outcomes (glucose, insulin, lipids, gut hormones and inflammatory markers levels) of individuals from 2 or 3 generations in direct link (grandmother, mother and daughter).

4. Primary Outcome:

Comparison of the change in SCFA production from baseline to the end of the intervention between grandmothers, mothers and daughters between dietary fibre intervention and placebo.

5. Secondary Outcomes:

- Comparison of gut microbiota composition from baseline to the end of the intervention between grandmothers, mothers and daughters between dietary fibre intervention and placebo.

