- Comparison of metabolic profiles of urine and stool samples from baseline to the end of intervention between grandmothers, mothers and daughters between dietary fibre intervention and placebo.
- Comparison of blood glucose levels from baseline to the end of intervention between grandmothers, mothers and daughters between dietary fibre intervention and placebo.
- Comparison of blood insulin levels from baseline to the end of intervention between grandmothers, mothers and daughters between dietary fibre intervention and placebo.
- Comparison of gut hormone levels from baseline to the end of intervention between grandmothers, mothers and daughters between dietary fibre intervention and placebo.
- Comparison of blood lipid levels from baseline to the end of intervention between grandmothers, mothers and daughters between dietary fibre intervention and placebo.
- Correlation of 3 days food diary information with gut bacteria production of SCFA among the 2 or 3 generations.

- Correlation of 3 days food diary information with gut bacteria composition among the 2 or 3 generations.
- Correlation of 3 days food diary information with urine metabolic profiles among the 2 or 3 generations.

6. Study methodology:

- Randomised, placebo controlled, double-blinded, cross-over study
- 4 weeks intervention (dietary fibre/placebo) 4 weeks wash-out 4 weeks intervention (opposite arm of intervention)

7. Intervention products:

The fibre intervention product will contain in equal proportions inulin, pectin and oat beta-glucan.

The placebo product will contain cellulose.

The intervention products will be sourced from Nestlé.

The fibre intervention and placebo products will be powders stored in sachets that will look identical and identically-packaged and participants will be able to add them to and mix them with their meals. The amount of intervention taken daily will be increased gradually (see below) to allow participants to adapt to the increased intake of dietary fibre and reduce the likelihood of gastrointestinal discomfort.

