Participants will be asked not to consume any intervention products on the study visit. At the end of study visits 1 and 3, participants will receive 56 sachets of intervention products. At study visits 2 and 4, participants will be asked to bring the empty sachets to assess compliance with the intervention. Throughout the 2 study intervention periods, participants will be asked to complete daily the Intervention Product Reminder sheet whenever they take the intervention product. This will also allow for assessing compliance with the intervention.

Intervention products will be stored in sachets and boxes in the Commonwealth Building of Hammersmith campus, Imperial College London.

8. Participants:

10 duos or trios (20-30 participants) females

Inclusion criteria:

- Any of the following groups of people (in direct descent and from the same family):
 - Grandmother, mother and daughter

- Mother and daughter
- Grandmother and granddaughter
- Age 18-85 (inclusive)
- BMI: 18.5-30 kg/m² (inclusive)
- Considering themselves healthy

Exclusion criteria:

- Intake of antibiotics in the past 3 months and during the study
- Intake of probiotic supplements in the past month and during the study
- Regular intake of laxatives in the past month and during the study
- Subjects with the following conditions:
 - Inflammatory Bowel Disease (IBD)
 - Irritable Bowel Syndrome (IBS)
 - Coeliac Disease
 - Type 12 Diabetes
 - Any type of cancer
 - Autoimmune conditions
 - Conditions that affect the liver
 - Conditions that affect the pancreas
- Subjects who require medical intervention in the coming 3 months
- Smokers
- Shift workers
- Gluten intolerance
- Pregnant and lactating women
- Subjects living in care homes
- had weight changes >5% in the preceding 3 months
- Subjects who are unable to give informed consent by themselves
- Subjects who are currently participating in other clinical trials

Support of number of volunteers:

This is a pilot exploratory study in a new area of research and therefore statistical power calculation is not possible.

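### Product order is not balanced by generation and no period term is planned, so chance imbalance in order costs precision in the primary generation contrast

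*Combined protocol and SAP*

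**What the plan says.** Section 6 describes a "Randomised, placebo controlled, double-blinded, cross-over study" with two four-week intervention periods separated by a four-week wash-out. Section 7 adds that "Randomization of study participants to the order in which they will receive the intervention products (placebo and dietary fibre) will be done by SealedEnvelope.com". Nothing in the document makes the family the unit of allocation, ties relatives to one order, stratifies by generation, or gives a block size or ratio.

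Section 4 sets the primary outcome as "Comparison of the change in SCFA production from baseline to the end of the intervention between grandmothers, mothers and daughters", contrasted between fibre and placebo. That is a generation-by-treatment comparison. Section 9 gives each period its own start and end visit (visits 1 and 2, then 3 and 4), so change is measured within each period.

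The sample in section 8 is "10 duos or trios (20-30 participants) females", with no power calculation. Section 11 plans paired and/or unpaired t-tests and ANOVA for SCFA at p<0.05, and names no period, sequence or family term.

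Section 7 also describes the products as "powders stored in sachets that will look identical and identically-packaged and participants will be able to add them to and mix them with their meals". Compliance is checked from returned empty sachets and a daily reminder sheet.

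**The concern.** In a two-period crossover, each woman's fibre-minus-placebo value contains her treatment response plus or minus any period effect, with the sign set by the product she took first. Averaged over one group with balanced orders, the period effect drops out. The primary question here compares groups, so it drops out only if the generations have the same mix of orders, or if the model removes it. The protocol provides for neither.

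With at most 10 women per generation, order can easily be unequal by chance. At stake is the precision of the one contrast the trial was built to estimate, in a sample with little to spare. Individual allocation would also often place relatives on opposite orders, which raises the question of sachets being mixed up or the blind being broken within a family.

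**Working it through.** There is no sample-size or power figure to reproduce. The only count, 10 × 2 = 20 to 10 × 3 = 30 women, is consistent.

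**Inputs.** From the documents: 10 families, two periods, two orders, a contrast between generations, and no period term. Assumed: simple 1:1 allocation to order; 10 women in each generation compared (the 30-woman maximum if all three are counted); a period effect equal in all generations; two-sided 5% tests.

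**Step 1: how the period effect enters.** Let P be the difference between periods 2 and 1 in the four-week SCFA change. A woman's fibre-minus-placebo value is τ + sP, where τ is her response and s = +1 or −1 by order. Between two relatives the period part is 0 if their orders match and ±2P if they differ.

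**Step 2: relatives on different orders.** P(a duo does not share one order) = 1 − 2(1/2)² = 0.50. For a trio it is 1 − 2(1/2)³ = 0.75. Of 10 families, 5.0 (all duos) to 7.5 (all trios) are expected to be split.

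**Step 3: shift in a two-generation contrast.** The shift is P × (difference in mean s). A gap of k fibre-first women out of 10 gives 2kP/10.

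- SD of the shift = P × √(1/10 + 1/10) = 0.447P, with mean 0.
- P(gap = 0) = 0.176.
- P(gap ≥ 2, shift ≥ 0.4P) = 0.503.
- P(gap ≥ 3, shift ≥ 0.6P) = 0.263.
- P(gap ≥ 4, shift ≥ 0.8P) = 0.115.

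Across three generations, the largest pairwise gap is 3 or more in 50.1% of simple allocations.

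**Step 4: does ordinary blocking help?** No. With 30 women balanced 15:15 overall, the two figures for a gap of 3 or more are 0.271 (a given pair of generations) and 0.467 (the largest of three). For 10 duos the SD of the shift is 0.458P with 10:10 overall balance, and 0.517P with blocks of 4 filled family by family, where about 67% of duos are split. Balance has to be imposed within generation.

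**Step 5: effect on the test.** A simulation used 10 pairs and a paired t-test, with within-woman difference SD 1, family correlation 0.3 and a true contrast of 1 SD (40,000 runs; all assumed values).

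| P (in SD) | Individual, no period term | Individual, period term | One order per family |
|---|---|---|---|
| 0 | 0.67 | 0.60 | 0.66 |
| 0.25 | 0.63 | 0.60 | 0.66 |
| 0.5 | 0.53 | 0.61 | 0.66 |
| 1 | 0.33 | 0.60 | 0.66 |

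The entries are power. Type I error was 0.048 to 0.052 in every cell, and the pattern was the same for family correlations of 0 and 0.5. As a check, the SD of the estimated contrast under individual allocation without a period term should be √(2(1 − 0.3)/10 + 0.2P²) = 0.374, 0.391, 0.436 and 0.583. The simulation gave 0.375, 0.393, 0.437 and 0.585.

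**Step 6: the cost of one order per family.** Relatives then carry the same-signed period effect. With residual SD 1 and no true family correlation, the apparent correlation between relatives is P²/(1 + P²): 0.06, 0.20 and 0.50 for P = 0.25, 0.5 and 1. Section 1 makes similarity of response within families a question of interest, so period must be modelled under this scheme as well.

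**The case against.** The strongest reply is that the protocol is silent rather than wrong. It calls the study an exploratory pilot with no power target, and the sponsor may intend a sensible list. The outcome is a change within each period, so a stable difference in level between periods is already subtracted; only a period difference in the four-week change matters, and that may be near zero. A period term would deal with it whatever the allocation. All of this stands. It limits the size of the problem but does not remove it, because the document neither balances order within generation nor plans the term.

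Three stronger readings are tempting and are not supported:

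- *That the generation contrast is biased.* The shift has expectation zero over allocations and type I error stays near 0.05. One realised allocation may be unlucky, but the procedure is not systematically distorted.
- *That the protocol must randomise by family, at no cost.* A shared order creates artificial family resemblance unless period is modelled, leaves only 10 allocated units, and reveals the whole family's order if one member is unblinded. Nor does it clear every contrast: section 8 admits two kinds of duo, section 12 lets relatives continue after one withdraws, and section 11 allows unpaired tests, so some comparisons would involve different families.
- *That relatives will hold opposite look-alike products at the same time and swap them or break the blind.* The documents do not say that relatives share a home or meals, or run their periods together; the family is described as attending together only for screening. This is a possible risk, not a demonstrated flaw.

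**Conclusion.** The concern holds as a matter of precision. On the natural reading of section 7, order is allocated to individuals without balance by generation, and section 11 does nothing to remove a period effect. With 10 women per generation and simple 1:1 allocation, two generations differ by 3 or more fibre-first women about 26% of the time, and the SD of the shift in their contrast is about 0.45 times the period effect on the four-week SCFA change.

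The practical loss depends on a period effect that the documents do not give. In the scenario above it runs from nothing at P = 0 to about half the power at P = 1 SD (0.67 to 0.33). The conclusion rests on individual 1:1 allocation, a period effect common to all generations, and full generations of 10. With fewer women in a generation, chance imbalance in the proportion of each order would be larger.

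**What to change.** 1. In section 7, state the unit of randomisation, the ratio, the strata and the blocking. Stratify the list by generation with small blocks. Blocks of 2 give exactly 5:5 in a generation of 10. Blocks of 4 leave two women in an unfinished block, so the split could be 6:4 in one generation and 4:6 in another, a gap of 2 and a shift of 0.4P.
2. In section 11, fit a period term and a family effect in the primary SCFA analysis. Stratification balances the generation means, but relatives can still have opposite orders, and without the term their ±2P differences inflate the error variance.
3. If the sponsor prefers one order per family (5 families in each order), that is acceptable. It sets the shift to zero in within-family contrasts of complete families, but it needs the same period term and carries the drawbacks given under the objection.
4. Add a sentence on how relatives' sachets are told apart and kept separate, as a precaution.

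The cost is a setting in the randomisation service and a few protocol sentences before enrolment. In the scenario above, the period term cost about 6 points of power when there was no period effect (0.67 to 0.60, rounded) under unbalanced individual allocation, with the effect estimated from pair differences alone. Every woman still receives both products.
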